3. OBJECTIVES, ESTIMANDS, AND ENDPOINTS

Objectives	Endpoints	Estimands
Primary:	Primary:	Primary:

 To investigate the efficacy of PF-06462700 administered intravenously at 40 mg/kg/day for 4 days in Japanese participants with moderate and above aplastic anemia 	
 Hematologic response at Week 12 	
Population: Japanese participants with moderate and above aplastic anemia who are at least 2 years of age
 
Variable: Hematologic response at Week 12
 
Intercurrent events: The efficacy will be evaluated individually for each patient. Therefore, any missing data will not be imputed. All observations after prohibited concomitant medication will be included. Improvement in counts that are dependent upon exogenously administered growth factors or transfusion will not be considered as fulfilling hematologic response criteria in the evaluation.
 
Population-level summary: Due to the limited sample size, summary statistics will not be shown.

Secondary:	Secondary:	Secondary:

 To investigate the efficacy of PF-06462700 administered intravenously at 40 mg/kg/day for 4 days in Japanese participants with moderate and above aplastic anemia 	
 Hematologic response at Week 24 Hematological test values at Day 4 and at Weeks 1, 2, 4, 6, 8, 10, 12 and 24 (Absolute neutrophil count, Platelet count, Reticulocyte count). In case of ET, at ET and follow-up ET. Survival status Transfusion independence at Weeks 12 and 24 	
Population: Japanese participants with moderate and above aplastic anemia who are at least 2 years of age
 
Variable: Each secondary endpoint
 
Intercurrent events: The efficacy will be evaluated individually for each patient. Therefore, any missing data will not be imputed. All observations after prohibited concomitant medication will be included.
 
Population-level summary: Due to the limited sample size, summary statistics will not be shown.

Safety objective:	Safety endpoints:	Estimands:

To investigate the safety of PF-06462700 administered intravenously at 40 mg/kg/day for 4 days in Japanese participants with moderate and above aplastic anemia	
Treatment-emergent adverse events (TEAEs)Serious AEs (SAEs) and AEs leading to discontinuationVital signsClinical laboratory values	N/A
---	--	-----

4. STUDY DESIGN

4.1. Overall Design

Study B5411003 will assess the efficacy and safety of PF-06462700 in participants with moderate and above aplastic anemia. This is a multicenter, open-label, single-arm study. The study will have a maximum duration of approximately 28 weeks. This includes an up to 4-week screening period, a 4-day treatment period and a 24-week follow-up period. This study will enroll the minimum of 3 participants. The study will be initially conducted at 3 sites.

To be eligible to enroll in this study, participants must have moderate and above aplastic anemia at screening visit. The full list of eligibility criteria for the study is included in Section 5.

Screening will occur within 28 days prior to the first dose of study drug to confirm that participants meet enrollment criteria for the study. Eligible participants will be administered to this investigational drug intravenously at 40 mg/kg/day for 4 days.

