Abbreviations: Ab = antibody; CMV = cytomegalovirus; EBV = Epstein-Barr virus; ECG = electrocardiogram; ET = Early Termination; HBV = hepatitis B virus, HCV = hepatitis C virus; HIV = human immunodeficiency virus; HTLV-1 = human T-cell leukemia virus type 1; → = ongoing/continuous event, WOCBP = woman of childbearing potential.

- Day relative to start of study treatment (Day 1).
- Hematology, Blood chemistry, Urinalysis, Coagulation, and Pregnancy test on Day 1 can be omitted, if the interval between Screening visit and Day 1 visit is within 7 days.
- For WOCBP only. Monthly urine pregnancy tests and contraception check will be performed by the participant between scheduled study visits starting after the Week 12 visit through the Week 24 or ET visit. Site personnel will contact participants (or their legally authorized representative, if appropriate) between study visits to obtain monthly pregnancy test result and ensure this contact and the result of the pregnancy test are recorded in participant source documentation and CRF.
- EBV DNA or CMV DNA will be performed at Weeks 2, 4, 6, 8, 10, 12 and 24, or ET, or Follow-up of ET for any participant who is EBV Ab or CMV Ab positive at screening.
- If there is body weight data within 3 days before baseline, it can be adopted as a baseline data.

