5.1. Inclusion Criteria

Participants are eligible to be included in the study only if all of the following criteria apply:

Age and Sex:

1. Male or female participants between the ages of 2 years and more, inclusive, at Visit 1 (Screening).
 - Refer to Appendix 4 for reproductive criteria for male (Section 10.4.1) and female (Section 10.4.2) participants.

Type of Participant and Disease Characteristics:

2. Participants who are willing and able to comply with all scheduled visits, treatment plan, laboratory tests, lifestyle considerations, and other study procedures.
3. Have a clinical diagnosis of aplastic anemia by bone marrow aspiration/biopsy findings and/or magnetic resonance imaging (MRI) etc.
4. Must meet the following criteria of moderate and above aplastic anemia (Stage 2b and above, see [Table 2](#)):

Informed Consent:

5. Capable of giving signed informed consent/assent as described in Appendix 1, which includes compliance with the requirements and restrictions listed in the informed consent document (ICD)/assent document and in this protocol.

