6.3. Measures to Minimize Bias: Randomization and Blinding

6.3.1. Allocation to Investigational Product

Registration will be performed centrally by the sponsor or designee for all participants. Following full assessment and determination that the participant meets all eligibility criteria, the investigator or designee will fax or email a complete the registration form to the sponsor or designee. The sponsor or designee will assign a participant identification number, which will be used on all case report form (CRF) pages and other trial-related documentation or correspondence referencing that participant and fax or email to the site.

No participant shall receive investigational product until the investigator or designee has received the above information from the sponsor or designee: confirmation of the participant's enrollment.

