8.1. Efficacy Assessments

8.1.1. Hematologic response

Hematologic response at Weeks 12 and 24

“Effective” when 2 or more of the following criteria:

- Absolute neutrophil count $\geq 500/\mu\text{L}$
- Platelet count $\geq 20,000/\mu\text{L}$
- Reticulocyte count $\geq 60,000/\mu\text{L}$

Improvement in counts that are dependent upon exogenously administered growth factors or transfusion will not be considered as fulfilling response criteria.

For subjects of Stage 2b or 3 (see [Table 2](#)) at the baseline*, hematological response will be “effective” when the above-mentioned criteria are met, and Stage is improved at the same time. (*If the baseline assessment is omitted [[Section 1.3](#)], severity at the screening will be referred.)

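### The stage-improvement condition covers only baseline Stage 2b or 3, so a participant measured at Stage 2a or 1 on Day 1 could be scored Effective with no change

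*Protocol*

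**What the plan says.** **Entry.** Protocol Section 4.1 states that "participants must have moderate and above aplastic anemia at screening visit" and that "Screening will occur within 28 days prior to the first dose of study drug to confirm that participants meet enrollment criteria for the study". Inclusion criterion 4 (Section 5.1) reads "Must meet the following criteria of moderate and above aplastic anemia (Stage 2b and above, see" and points to Table 2; it carries no date. Section 6.3.1 places registration after the site has judged eligibility: "Following full assessment and determination that the participant meets all eligibility criteria". The Schedule of Activities puts registration on Day 1.

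**Response.** Section 8.1.1 and SAP Section 3.1 call a participant Effective "when 2 or more of the following criteria" are met: neutrophils at least 500, platelets at least 20,000, reticulocytes at least 60,000 per µL. These are absolute levels, not changes. An extra condition follows. "For subjects of Stage 2b or 3" at baseline, response counts as Effective "when the above-mentioned criteria are met, and Stage is improved at the same time". SAP Section 3.2.1 applies the same definition at Week 24.

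**Baseline.** Baseline is Day 1. A Schedule of Activities footnote says that Day 1 hematology "can be omitted, if the interval between Screening visit and Day 1 visit is within 7 days"; in that case Section 8.1.1 uses the screening severity. Neither document has a rule for a baseline of Stage 2a or Stage 1.

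**The concern.** The count thresholds sit at the severe-disease cut-offs for neutrophils and platelets, so people with milder disease can meet them before any treatment. The plan recognises this and adds the stage-improvement condition, but the condition names only two stages. When screening and Day 1 are both measured, the stage that admitted the participant and the stage that serves as baseline come from different blood samples. If the second one is 2a or 1, the safeguard does not apply and an unchanged participant receives the favourable label on the primary endpoint.

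The study is single-arm, supports an approval application and targets 3 participants. One mislabelled case would be 1/3 of the target sample, or less if more than 3 are treated.

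**Working it through.** The plan states no figure for this point (the sample size of 3 rests on feasibility), so the check is one of logic.

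**Inputs.** Table 2 gives the stage cut-points: for Stages 2 and 3, reticulocytes 60,000, neutrophils 1,000 and platelets 50,000; for Stage 4, 40,000, 500 and 20,000 (all per µL). Section 8.1.1 gives the response thresholds listed above.

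**Step 1: which measurement is the baseline.**
- Screening 8 to 28 days before Day 1: Day 1 hematology is mandatory and sets the baseline stage.
- Screening within 7 days and Day 1 hematology omitted: the screening stage is the baseline. It is 2b or above for anyone who meets criterion 4, so this gap does not arise.

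**Step 2: count patterns.** Split each count into low, mid and high at its two cut-points, giving 3 × 3 × 3 = 27 patterns.
- Stage 4 or 5 needs at least two low counts: 3 × 2 + 1 = 7 patterns.
- The Stage 2 and 3 count condition needs at least two counts that are low or mid: 3 × (2 × 2 × 1) + 2 × 2 × 2 = 20. Removing the 7 above leaves 13, which are Stage 2a if no red-cell transfusion is required.
- The remaining 27 − 20 = 7 are Stage 1 if no red-cell transfusion is required.

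**Step 3: which patterns already meet 2 of 3.** The response thresholds are met by neutrophils mid or high, platelets mid or high, and reticulocytes high.
- Stage 2a with no low count (4 patterns): neutrophils and platelets both qualify, so 4 meet the rule.
- Stage 2a with one low count (9 patterns): reticulocytes low, 3 of 3; neutrophils low, 1 of 3 (needs high reticulocytes); platelets low, 1 of 3 (same reason).
- Stage 2a total: 4 + 3 + 1 + 1 = 9 of 13.
- Stage 1: at least two counts are high, and each of those qualifies, so 7 of 7.
- Stage 4 or 5: at least two counts are low, so at most one can qualify, giving 0 of 7. This holds under both the protocol and the SAP wording of Stage 5.

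| Baseline | Patterns meeting 2 of 3 unchanged | Stage must improve? |
|---|---|---|
| Stage 1 | 7 of 7 | not stated |
| Stage 2a | 9 of 13 | not stated |
| Stage 2b, 3 | 9 of 13 (same count condition) | yes |
| Stage 4, 5 | 0 of 7 | not needed |

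A finer split at every cut-point (4 × 4 × 3 = 48 patterns) gives 13 of 19 for Stage 2a, 9 of 9 for Stage 1 and none for Stages 4 and 5. The Stage 2a ratio depends on the grid; the conclusion does not.

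**Step 4: one case followed through (illustrative values).**
- Screening: neutrophils 480, platelets 19,000, reticulocytes 50,000. Two counts are below the severe cut-offs: Stage 4, meets criterion 4.
- Day 1: neutrophils 520, platelets 21,000, reticulocytes 50,000, no red-cell transfusion. No count is below a severe cut-off and all three are below the moderate ones: Stage 2a.
- Week 12: identical to Day 1. Neutrophils and platelets meet their thresholds, and the stage condition does not apply: Effective.

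**Step 5: after the fix.** With stage improvement required of every baseline below Stage 4, an unchanged Stage 2a participant is no longer Effective. With Stage 1 ruled out explicitly, the unchanged patterns fall from 9 and 7 to 0 and 0.

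**The case against.** **Entry may be checked on Day 1.** Criterion 4 is undated, whereas criterion 1 is dated to screening. Registration is on Day 1, after all criteria are judged met; the skin test behind exclusion 8 is also on Day 1; and waivers are barred. On that reading a known Day 1 Stage 2a participant is ineligible, and naming only Stages 2b and 3 is complete. This stands in part. A site may re-stage, so a reader should not infer that the plan rules out a Day 1 severity check. But no sentence requires one, and Section 4.1 points to screening.

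**The route is narrow.** It needs a measured Day 1 stage, no red-cell transfusion requirement, and counts that cross cut-offs before dosing. This stands.

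**The case would be visible.** No test or response rate is planned. SAP Sections 6.1.1.1 and 6.4.1 list severity and counts at Week 12 and at baseline. This also stands, but the printed label would still be Effective, and the SAP defines no sensitivity analysis or analysis-related deviation that would change it.

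**Stronger readings that the documents do not support.**
- A reader might infer a regression-to-the-mean problem that confirming severity on Day 1 would cure. Selecting on the same value that serves as baseline does not reduce regression to the mean. Someone at 480 and 19,000 on Day 1 and 520 and 21,000 at Week 12 is Effective under either rule.
- A reader might infer that a Stage 2b participant with a transfusion-free month before Day 1 becomes Stage 2a. Table 2 defines 2b by a frequency below 2 units per month and sets no one-month look-back.
- A reader might take 9 of 13 to mean that most such patients already qualify. Unweighted patterns say nothing about how patients are distributed.

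**Conclusion.** The gap is real and limited. As written, a participant with a measured Day 1 stage of 2a or 1 is scored on absolute counts alone and can be Effective at Week 12 or 24 with no change: possible in 9 of 13 Stage 2a and 7 of 7 Stage 1 patterns, and in none at Stage 4 or 5. This rests on three assumptions: that the response rule is applied literally, that baseline is Day 1 when measured, and that a site relying on Section 4.1 treats the participant. The documents give no rate for stage shifts within 28 days, so no probability can be attached. It is an incomplete primary endpoint definition that should be closed; it does not show that any participant will be mislabelled.

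**What to change.** 1. In Protocol Section 8.1.1 and SAP Section 3.1, apply the stage-improvement condition to every participant below Stage 4 at baseline, not only Stages 2b and 3. State that a Stage 1 baseline cannot be scored Effective, since no lower stage exists. Week 24 follows through SAP Section 3.2.1.
2. Separately, reconcile Section 4.1 with criterion 4. Section 4.1 says moderate and above at screening, and Table 2's moderate category includes 2a; criterion 4 says 2b and above with no date. The sponsor should settle which stage and which time point apply. If that choice rules out a Day 1 stage below 2b, item 1 matters only for deviations but still completes the definition.

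**Cost.** No visit or sample is added. The primary endpoint wording changes, so a protocol amendment is needed (Section 9) with ethics committee approval (Section 10.1.1). A participant who improved before dosing and then held steady could be scored a non-responder.

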4.2. Scientific Rationale for Study Design

This study's objectives are to investigate the efficacy and safety of PF-06462700 administered intravenously at 40 mg/kg/day for 4 days in each of Japanese patients with aplastic anemia. The study design of this study was set according to the study design of the NIH-initiated clinical study¹. Since this disease is a serious and rare disease, the target sample size was set to be 3 subjects from the viewpoint of feasibility, and the study was designed as a single-arm, open-label study in a group treated with PF-06462700. This study design was agreed upon with PMDA on CCI [REDACTED].

4.3. Justification for Dose

Based on the development request for this drug by the Research and Development Division, Health Policy Bureau, Ministry of Health, Labor and Welfare (MHLW), the dosage and administration intravenously of 40 mg/kg/day for 4 days should be selected for this study. This dosage and administration is the same as the NIH-initiated study demonstrated that PF-06462700 provided a significantly higher 6-month haematologic response and 3-year survival rate than comparable treatment with rabbit-ATG.

4.4. End of Study Definition

A participant is considered to have completed the study if he/she has completed all phases of the study including the last visit.

The end of the study is defined as the date of the last visit of the last participant in the study.

5. STUDY POPULATION

This study can fulfill its objectives only if appropriate participants are enrolled. The following eligibility criteria are designed to select participants for whom participation in the study is considered appropriate. All relevant medical and nonmedical conditions should be taken into consideration when deciding whether a particular participant is suitable for this protocol.

Prospective approval of protocol deviations to recruitment and enrollment criteria, also known as protocol waivers or exemptions, is not permitted.

5.1. Inclusion Criteria

Participants are eligible to be included in the study only if all of the following criteria apply:

Age and Sex:

1. Male or female participants between the ages of 2 years and more, inclusive, at Visit 1 (Screening).
 - Refer to Appendix 4 for reproductive criteria for male (Section 10.4.1) and female (Section 10.4.2) participants.

Type of Participant and Disease Characteristics:

2. Participants who are willing and able to comply with all scheduled visits, treatment plan, laboratory tests, lifestyle considerations, and other study procedures.
3. Have a clinical diagnosis of aplastic anemia by bone marrow aspiration/biopsy findings and/or magnetic resonance imaging (MRI) etc.
4. Must meet the following criteria of moderate and above aplastic anemia (Stage 2b and above, see [Table 2](#)):

Informed Consent:

5. Capable of giving signed informed consent/assent as described in Appendix 1, which includes compliance with the requirements and restrictions listed in the informed consent document (ICD)/assent document and in this protocol.

5.2. Exclusion Criteria

Participants are excluded from the study if any of the following criteria apply:

Medical Conditions:

1. Eligible and willing to have a sibling allogeneic stem cell transplantation.

2. Evidence of a myelodysplastic syndrome (except for refractory cytopenia in children), as well as other primitive marrow disease.
3. History or clinical suspicion of congenital aplastic anemia (Fanconi anemia, Congenital keratosis, etc).
4. History of malignant tumors with active disease within 5 years from study participation.
5. Participants who are clearly infected with hepatitis B virus (HBV), hepatitis C virus (HCV), human immunodeficiency virus (HIV), and human T-cell leukemia virus type 1 (HTLV-1).
6. Pregnant or breast-feeding participants.
7. Participants with severe hepatic, renal or cardiac failure, or any other life-threatening concurrent [aspartate aminotransferase (AST) or alanine aminotransferase (ALT) or total bilirubin values $>5 \times$ upper limit of normal (ULN), and/or creatinine value $>2 \times$ ULN].
8. Participants with hypersensitivity such as shock after skin test of this study drug.
9. Participants with uncontrolled severe infection (pneumonia, sepsis, etc).
10. Participants who received live vaccine or live attenuated vaccine within 6 weeks prior to the first dose of study drug.
11. Other acute or chronic medical or psychiatric condition including recent (within the past year) or active suicidal ideation or behavior or laboratory abnormality that may increase the risk associated with study participation or investigational product administration or may interfere with the interpretation of study results and, in the judgment of the investigator, would make the participant inappropriate for entry into this study.

Prior/Concomitant Therapy:

12. Prior immunosuppressive therapy with lymphocyte-depleting agents/therapies, including both non-B-cell selective and B-cell-depleting agents (e.g., alefacept, alemtuzumab, rituximab). However, participants previously treated with rATG may enroll.
13. Previous history of stem cell transplantation.

Prior/Concurrent Clinical Study Experience:

14. Previous administration with an investigational drug within 30 days (or as determined by the local requirement) or 5 half-lives preceding the first dose of investigational product used in this study (whichever is longer).

Diagnostic Assessments:

15. Baseline 12-lead electrocardiogram (ECG) that demonstrates clinically relevant abnormalities that may affect participant safety or interpretation of study results (e.g., baseline corrected QT [QTc] interval >450 msec, complete left bundle branch block [LBBB], signs of an acute or indeterminate-age myocardial infarction, ST-T interval changes suggestive of myocardial ischemia, second- or third-degree atrioventricular [AV] block, or serious bradyarrhythmias or tachyarrhythmias). If the baseline uncorrected QT interval is >450 msec, this interval should be rate-corrected using the Fridericia method and the resulting QTcF should be used for decision making and reporting. If QTc exceeds 450 msec, or QRS exceeds 120 msec, the ECG should be repeated 2 more times and the average of the 3 QTc or QRS values should be used to determine the participant's eligibility. Computer-interpreted ECGs should be overread by a physician experienced in reading ECGs before excluding participants.

Other Exclusions:

16. Investigator site staff members directly involved in the conduct of the study and their family members, site staff members otherwise supervised by the investigator, or Pfizer employees, including their family members, directly involved in the conduct of the study.

5.3. Lifestyle Considerations

5.3.1. Contraception

The investigator or his or her designee, in consultation with the participant, will confirm that the participant has selected an appropriate method of contraception for the individual participant from the permitted list of contraception methods (see [Appendix 4: Contraceptive Guidance and Collection of Pregnancy Information Section 10.4.4](#)) and will confirm that the participant has been instructed in its consistent and correct use. At time points indicated in the schedule of activities (SoA), the investigator or designee will inform the participant of the need to use highly effective contraception consistently and correctly and document the conversation and the participant's affirmation in the participant's chart (participants need to affirm their consistent and correct use of at least 1 of the selected methods of contraception). In addition, the investigator or designee will instruct the participant to call immediately if the selected contraception method is discontinued or if pregnancy is known or suspected in the participant or partner.

